14.2 Secondary Endpoint Analysis

All secondary endpoints will be analyzed for the Intent-To-Treat (ITT) population with a Per-Protocol (PP) sensitivity analysis.

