- 200 mL/hr for a 100 mL IV bag

Step 4:

Flush the IV line according to local practices to ensure the full dose is administered. Infusion time does not include the final flush time. Flush the catheter with 0.9% sodium chloride for injection at the end of the infusion.

- Site personnel may administer AZD7442 600 mg IV ONLY under one of or more of the following conditions:
 - at the discretion of the Investigator if the patient would have less discomfort with an intravenous route (i.e., has significant weight loss and little gluteal or thigh muscle mass)
 - if the patient already has an indwelling medication “port” through which the patient receives intravenous drug administration.
 - if the patient’s platelet count $\leq 50,000/\mu$ l
 - if the patient has a history of a coagulation disorder
- AZD7442 may only be administered by IV infusion in settings in which healthcare providers have immediate access to medications to treat a severe infusion reaction, such as anaphylaxis, and the ability to activate the emergency medical system as necessary.
- Patients administered AZD7442 IV will be observed for immediate side effects and have vital signs measured every 15 minutes during the time of infusion and for the 60 minutes following the end of the infusion. All such vital signs will be record in the patient’s medical record.
- If an infusion-related reaction occurs, the AZD7442 infusion should be immediately terminated and appropriate medications including but not limited to diphenhydramine, other anti-histamines, methylprednisolone, epinephrine and/or other supportive care measures should be immediately provided.

- Patients will be observed for immediate side effects for 60 minutes following AZD7442 600 mg IM administration
- Site personnel will give all patients one SARS-CoV-2 Home Test Kit for at home testing of possible SARS-CoV-2 infection at the conclusion of the baseline visit
- Automatic request for patient medical records, pharmacy fill/refill data and medical insurance claims data for the 6 months prior to baseline will be sent and forwarded to MediMergent for analysis

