- Time to first event (e.g., SARS-COV-2 RNA by RT-PCR positivity, symptomatic SARS-CoV-2 infection, hospitalization, death) post-treatment compared between all four strata
- Quality-of-Life metrics in all cancer patients, as measured by change from baseline to days 30, 90, 180, 270 and 360 post-baseline, compared between each of the four strata
- Patient symptom safety and rate of adverse events including medically attended visits, ER/urgent care/unplanned telehealth visits using Patient Experience/COA survey data summarized and compared in each of the four strata
- Incidence of AZD7442-related side effects compared between solid tumor and hematologic malignancy disease cohorts
- Predict the incidence of SARS-CoV-2 infection based on serum concentration of AZD7442 at days 30, 90, 180, 270 and 360 post-baseline in all cancer patients using machine learning algorithms.

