17.4 Populations for Analysis

The study will analyze two populations as defined by Intent-To-Treat (ITT) and Per Protocol (PP) criteria.

- The ITT population includes all participants who complete enrollment, complete the baseline Patient Experience/COA survey, baseline QoL assessment, baseline SARS-CoV-2 RBD-IgG, undergo AZD7442 600 mg IM or IV administration, complete at least one serum concentration AZD7442 measurement post-baseline AZD7442 administration, one RBD-IgG post-baseline, complete the Day 30 T-Cell assay, complete at least one follow-up Patient Experience/COA survey and one QoL assessment.
- The PP population includes all participants who complete all AZD7442 600 mg IM or IV administrations, complete the baseline Patient Experience/COA surveys, complete the baseline QoL assessment, complete the baseline SARS-CoV-2 RBD-IgG antibody level, complete the Day 30 and Day 210 T-Cell assay, complete 75% of follow-up Patient Experience/COA surveys, 75% of QoL assessments, 75% of RBD-IgG antibody levels and 75% of serum concentration of AZD7442 measurements post-baseline AZD7442 administration.

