17.9 Clinical Outcome Measurements

All other clinical outcome measurements will be analyzed for the ITT AZD7442 600 mg IM or IV treated groups for both solid tumor and hematologic malignancy population with a Per-Protocol (PP) sensitivity analysis. These include:

- Rate of symptomatic SARS-CoV-2 infection including hospitalization and/or death
- Rate of adverse events reported by the patient or investigator across the entire study observation period
- Rate of symptoms and change from baseline in symptom severity over the observed time points. Correlation of symptom severity with log-adjusted serum concentration of AZD7442 levels, defined as the change over time from first measurement at Day 30 to Days 90, 180, 270 and 360.
- Change in log-adjusted serum concentration of AZD7442 levels, defined as the change over time from first measurement at Day 30 to Days 90, 180, 270 and 360, relative to change in clinical status for individual disease category cohorts
- Clinical treatment outcomes such as treatment discontinuation and time to treatment progression where possible
- Health care resource utilization rates for ER, urgent care, hospitalization and unplanned telehealth visits
- Rate of death will also be considered if there is sufficient information for analysis
- Factor analysis to determine which factors (e.g., age, gender, type of cancer, cancer duration, type treatment, etc.) are related to higher levels of serum concentration of AZD7442

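### The Per-Protocol sensitivity set for event and safety outcomes leaves out, by construction, deaths before about Day 265 and reactions or withdrawals that prevent completion of both doses

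*Protocol*

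**What the plan says.** The rule for secondary endpoints is in Protocol Section 14.2: "All secondary endpoints will be analyzed for the Intent-To-Treat (ITT) population with a Per-Protocol (PP) sensitivity analysis". Section 17.6 repeats it. The secondary endpoints in Section 14.1 include symptomatic infection with related hospitalization or death, and also:

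- "Time to first event (e.g., SARS-COV-2 RNA by RT-PCR positivity, symptomatic SARS-CoV-2 infection, hospitalization, death) post-treatment compared between all four strata"
- "Incidence of AZD7442-related side effects compared between solid tumor and hematologic malignancy disease cohorts"

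Section 17.9 covers the remaining outcomes: "All other clinical outcome measurements will be analyzed for the ITT AZD7442 600 mg IM or IV treated groups", and the same sentence adds a PP sensitivity analysis. Its list includes the rate of symptomatic infection, the rate of death if there is enough information, and "Rate of adverse events reported by the patient or investigator across the entire study observation period".

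Section 17.4 sets the entry conditions: "The PP population includes all participants who complete all AZD7442 600 mg IM or IV administrations". The same item also asks for the baseline measures, the Day 30 and Day 210 T-cell assays, 75% of follow-up surveys, 75% of QoL assessments, and "75% of RBD-IgG antibody levels and 75% of serum concentration of AZD7442 measurements post-baseline AZD7442 administration". It makes no exception for patients who die or who stop because of an adverse event, and the protocol names no other sensitivity set for these endpoints.

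On dosing, Section 9.3 places the second dose at Day 180 for all patients. For IV administration Section 9.2 says: "If an infusion-related reaction occurs, the AZD7442 infusion should be immediately terminated". Section 25.18 allows withdrawal for an adverse event at any time.

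**The concern.** A sensitivity analysis should show whether the main result survives a reasonable change of assumption. Here, entry to the set depends on surviving, on tolerating both doses and on staying under observation for about nine months. Those conditions are partly the outcomes being measured. A patient who dies on Day 200 contributes no death to the PP analysis of death, and a patient whose dosing is stopped by a reaction contributes no reaction to the PP analysis of side effects. Agreement between PP and ITT on these two kinds of event could then be taken as reassurance that it does not give.

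The loss need not be equal across groups. Section 23.1 cites an increased risk of death of at least 2.5-fold in hematologic malignancy. If something similar applied here, PP would drop proportionally more hematologic patients from the solid-versus-hematologic comparisons. Tolerability matters too, because Section 2.2 expects side effects not to differ between the four therapy strata.

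This is not a detail left to the statistical analysis plan: the protocol itself fixes both the set and its use.

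**Working it through.** The protocol gives no figure for this point, so there is none to reproduce. The check asks on which day a patient can first qualify for PP.

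**Step 1. Earliest day each 75% rule can be met.** The schedules are in Sections 5.5 and 9.3, with a window of ±5 days. The number needed is 0.75 × the number scheduled, rounded up.

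| Component | Scheduled days | 75% | Needed | Day reached |
|---|---|---|---|---|
| Concentration | 30, 90, 180, 270, 360 | 3.75 | 4 | 270 |
| RBD-IgG, post-baseline | 90, 180, 270, 360 | 3.0 | 3 | 270 |
| Follow-up surveys | 2, 30, 60, 90, 120, 150, 180, 181, 210, 240, 270, 300, 330, 360 | 10.5 | 11 | 270 |
| QoL, follow-up | 30, 90, 180, 270, 360 | 3.75 | 4 | 270 |

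Counting the baseline measure does not change the day: RBD-IgG 4 of 5, surveys 12 of 15 and QoL 5 of 6 are all reached at Day 270. With the window, 270 − 5 = Day 265. Any one of the four rules gives this alone, so it remains if the Day 210 T-cell criterion is removed. Even if extra draws at a breakthrough infection counted toward concentration and RBD-IgG, the survey and QoL rules would still require Day 265.

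**Step 2. A more lenient reading.** Suppose 75% means 75% of the assessments due so far. The Day 210 assay still excludes deaths before 210 − 5 = Day 205. Without that assay, the second dose still excludes deaths before 180 − 5 = Day 175.

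**Step 3. Share of deaths excluded.** With risk spread evenly over 360 days (assumption), 265/360 = 74% of all deaths fall before Day 265. With a constant hazard and 12-month all-cause mortality q (assumed; not in the protocol), the expected number among 1,500 patients is 1,500 × [1 − (1 − q)^(265/360)]:

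| Assumed q | All deaths | Before Day 265 | Share |
|---|---|---|---|
| 2% | 30 | 22 | 74% |
| 10% | 150 | 112 | 75% |
| 20% | 300 | 227 | 76% |

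**Step 4. Loss beyond ITT.** The ITT set in Section 17.4 requires the Day 30 T-cell assay and one post-baseline RBD-IgG, first scheduled at Day 90, or Day 85 with the window. Most deaths before Day 85 are therefore missing from ITT as well, unless an infection-triggered draw was taken. Under even risk, the further share lost in moving from ITT to PP is (265 − 85)/(360 − 85) = 180/275 = 65%.

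**Step 5. Dosing.** A patient whose first or second dose is stopped by a reaction, or who is withdrawn before the second dose, has not completed all administrations and cannot enter PP. The number of such patients cannot be derived from the protocol.

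**The case against.** PP is only a supporting analysis, ITT is the main one, and any completer set loses early deaths and discontinuations. That is true and limits the consequence. It is not a full answer, because the ITT set is itself conditional on early follow-up (step 4). The one planned check makes the same kind of exclusion, later and more heavily.

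Four stronger readings are tempting, and the protocol does not support them.

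- *PP always makes AZD7442 look safer and more protective, or carries no information.* There is no untreated arm, and most of these endpoints compare patient groups, so bias depends on differential exclusion of unknown direction. Section 9.3 follows infected patients to Day 360, so non-fatal infections stay in. PP incidence can even exceed ITT. Assume 10% infection risk per year, with 20% of patients leaving near Day 130. The crude ITT proportion is 0.8 × 10% + 0.2 × (130/360 × 10%) = 8.7%, against about 10% in PP.
- *PP would statistically rule out the true rate of dose-stopping reactions.* Suppose 15 of 1,500 patients (1.0%) had one. An upper 95% limit of 0.25% comes from 0/1,485, which ignores the Day 210 assay. Sections 5.5 and 9.3 draw that assay in only 120 + 60 = 180 patients, and 0/180 gives 1 − 0.025^(1/180) = 2.0%, which does not exclude 1.0%. The 15 is invented, and the termination rule in Section 9.2 concerns infusions only.
- *Every infection, death and safety result is affected.* Sections 14.3, 15.1, 17.10 and 18.1 carry no PP restriction.
- *The 14.9% mortality in Section 23.1 sizes the loss.* It comes from a cited study of patients with cancer and COVID-19. This trial excludes ECOG 2 or higher and expected survival under 12 months, which should lower the number of deaths but does not remove them.

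**Conclusion.** The point holds for the outcomes that Sections 14.2, 17.6 and 17.9 assign to PP. With the 75% rules read against the full schedule, PP contains no death before about Day 265, and no reaction or withdrawal that prevented completion of both doses. Deaths and dose-stopping reactions are therefore understated in that analysis. Non-fatal events in patients who remain on study are counted, though in a selected group, and the direction of bias in the between-group comparisons cannot be stated.

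The size for deaths is about 74% of all deaths, or about 65% beyond what ITT already loses. Both rest on even risk over 360 days; the 65% also treats every death before Day 85 as missing from ITT. No size can be given for side effects. The flaw does not overturn the main analysis, but it leaves these endpoints with a sensitivity analysis that conditions on survival and tolerability.

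**What to change.** In Sections 14.2, 17.6 and 17.9, restrict the Section 17.4 PP set to the concentration, RBD-IgG and QoL endpoints.

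For infection, hospitalization, death and time to first event, define the sensitivity set by eligibility and AZD7442 received, follow patients from Day 1, and drop the 75% and assay-completion rules. This also brings back early deaths that the ITT definition leaves out. If follow-up is censored at a dosing deviation, present that as an additional analysis only, because a deviation caused by a reaction may make the censoring informative.

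Analyse adverse events and AZD7442-related side effects in all patients who received any amount of AZD7442.

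The cost is wording and a little programming, with no new visits, samples or patients. The small downside is that the sensitivity set then differs by type of endpoint.

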14.3 Exploratory Endpoints

	
 • Determine the level of immunity (prevention of SARS-CoV-2 positive infection) over time provided by a combination of AZD7442 and antibodies that developed in response to prior SARS-CoV-2 vaccination or infection in this population. • Compare the AZD7442 serum concentrations and SARS-CoV-2 RBD-IgG antibody level collected prior to the event in subjects who do not develop SARS-CoV-2 infection versus those who develop SARS-CoV-2 infection overall and/or those who are hospitalized or die due to SARS-CoV-2 infection. • Virologic surveillance to detect all SARS-CoV-2 variants occurring during the study in patients that test positive for SARS-COV-2 RNA by RT-PCR (polymerase chain reaction) testing • Detection of potential new variants identified by positive SARS-COV-2 RNA by RT-PCR testing • Correlation of type of cancer and clinical stability with the following baseline and follow-up data: 
 ➤ Baseline immunologic profile consisting of spike antibody (SARS-CoV-2 RBD-IgG) data and T-cell function data (CD4 and CD8 analyses) • SARS-CoV-2 clinical outcomes including: 
 ➤ SARS-COV-2 RNA by RT-PCR positive test (symptomatic SARS-CoV-2 infection) ➤ Highest WHO SARS-CoV-2 Severity Classification ➤ TACKLE definition of severe SARS-CoV-2infection (pneumonia or hypoxemia, and WHO score of ≥ 5) ➤ Requirement for mechanical ventilation ➤ Death associated with SARS-CoV-2 infection
	
15.1 Interim Analysis
 
The interim analysis will be conducted in order to determine whether AZD7442 prevents a SARS-CoV-2 infection in the first 6 months post-treatment in solid tumor and/or hematologic malignancy patients. If break-through infections occur,


15.0 Interim Analysis
	
the analysis will determine which group is more likely to experience such infections.
 
An interim analysis will be performed after the first 6-month assessments are completed for the first 50% of the targeted patient sample for each malignancy, i.e., 750 patients including 600 solid tumor and 150 hematologic malignancies. The primary endpoint of the interim analysis will be the serum concentration of AZD7442 for all patients with comparisons between disease categories.
 
Secondary analyses will be conducted on the following measures in all patients included in the interim analysis set:
 
 • Incidence of break-through infections in all patients and then sub-divided into solid tumor and hematologic malignancy. • Time to infection compared between solid tumor and hematologic malignancy • RBD-IgG levels for all patients with comparisons between disease category • CD4/CD8 levels for all patients with comparisons between disease category

16.0 Immunological Sub-Study Endpoints
	
16.1 Immunologic Sub-Study Endpoints
 
 • Comparison of CD4 T-cell and CD8 T-cell function in all cancer patients at 30 days post initial administration of AZD7442 to similar tests performed in normal healthy donor subjects • Comparison of the relationship between different cancer treatment regimens and T-cell function in all cancer patients at 30 days post administration of AZD7442 • Comparison of the relationship between type of cancer (solid vs. hematologic) and T-cell function in all patients at 30 days post administration of AZD7442 • Comparison of the immunologic profile relating to AZD7442 serum level and T-cell function at the time of PCR positive SARS-CoV-2 infection in all cancer patients to Day 30 T-cell functionality • Comparison of the relationship between change from Day 30 in AZD7442 serum level, T- cell function and World Health Organization Ordinal Scale

	
(WOS) for SARS-CoV-2 disease severity in all cancer patients with documented PCR positive SARS-CoV-2 infection
 
 • Comparison of the relationship between change from Day 30 in AZD7442 serum level, T- cell function and World Health Organization Ordinal Scale (WOS) for SARS-CoV-2 disease severity in all cancer patients with documented RT-PCR positive SARS-CoV-2 infection based on type of cancer treatment.

17.0 Statistical Considerations
	
17.1 Sample Size Estimation
 
This program will recruit approximately 1,500 treated cancer patients divided into approximately 1,200 qualified solid tumor and 300 qualified hematologic malignancy patients from approximately 75 hematology/oncology medical practice locations throughout the United States. It is expected that on average, each site will enroll 16 solid tumor and 4 hematologic malignancy patients.
 
17.2 Sample Size Power
 
With a sample size of 1500 patients, the power to detect a non-inferiority margin of 5 mcg/ml with a standard deviation of 25 mcg/ml and Type I error rate of 1% is estimated to be approximately 80% when comparing the serum concentration levels between solid tumor and hematologic malignancy groups. The assumed comparison is between 1200 solid tumor and 300 hematologic malignancy patients. A target sample of 1500 patients will provide adequate size to analyze all of the secondary endpoints identified in the baseline and follow-up patient experience/COA surveys and the QoL surveys.
 
At the time of interim analysis, the power to detect a 5 mcg/ml non-inferiority margin with a standard deviation of 25 mcg/ml and Type I error rate of 1% is estimated to be approximately 45%. This assumes a sample of 600 solid tumor and 150 hematologic malignancy patients.
 
17.3 Stratification
 
This is an open-label, pragmatic, multi-center study of participants receiving AZD7442 600 mg IM or IV for prevention of symptomatic SARS-CoV-2 infection including SARS-CoV-2 related hospitalization and/or SARS-CoV-2 related death.

Patients will be stratified based on type of cancer (solid tumor vs hematologic malignancy) with additional stratification for concomitant treatment regimen of chemotherapy only, immunotherapy only, targeted therapy only and other therapy/combination therapy. It is assumed that 80% of enrolled cancer patients will have solid tumors. Patients will be sub-stratified by: currently on active treatment, ≤ 3 months post-treatment or > 3 months and ≤ 12 months post-treatment.

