
Clinical Hypotheses to be Evaluated
	
The primary clinical hypothesis to be evaluated is that in patients treated for either solid tumor or hematologic malignancy cancer, a dose of AZD7442 600 mg IM or IV every 6 months will prevent symptomatic SARS-CoV-2 infection including SARS-CoV-2 related hospitalization and/or SARS-CoV-2 related death, independent of type of cancer therapy up to 12 months post-dose. The possibility of a break-through SARS-CoV-2 infection may be influenced by type of cancer, current cancer treatment or length of time post-baseline administration of AZD7442.
 
2.2 Serum Concentrations of AZD7442
 
We hypothesize that serum concentrations of AZD7442 will not be different between solid tumor or hematologic malignancy treatment regimens at any time point post-baseline. We believe that serum concentration of AZD7442 may be correlated with IgG antibody level to SARS-CoV-2 and CD4/CD8 level as a measurement of T-Cell function as well as symptomatic SARS-CoV-2 infection, including SARS-CoV-2 related hospitalization and/or SARS-CoV-2 related death. We also expect to find that AZD7442 side-effects will not be significantly different between the four strata of cancer therapy (chemotherapy only, immunotherapy only, targeted therapy only, other therapy/combination therapy only).
 
2.3 T-Cell Function
 
We hypothesize that T-cell function obtained at Day 30 post AZD7442 administration in cancer patients will be within the normal range compared to historical healthy control patients' CD4/CD8 data. In addition, we hypothesize that patients who experience breakthrough SARS-CoV-2 infection will have an increase in T-cell function compared to data acquired on Day 30 post AZD7442 administration and that this increase will be in the range of expected results in historical control patients.

3.0 Study Objectives
	
3.1 Primary Objective:
 
The primary objective is to quantify the serum concentration of AZD7442 at 1,3, 6, 9 or 12-months post-baseline in all qualified cancer patients treated with AZD7442 600 mg IM or IV every 6 months.
 
3.2 Secondary Objectives:
 
The secondary objectives of the study are as follows:

- Compare the incidence of symptomatic SARS-CoV-2 infection including SARS-CoV-2 related hospitalization and/or SARS-CoV-2 related death between solid tumor and hematologic malignancy patients.

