	
 ➤ Patient who is unwilling to complete baseline and up to 5 follow-up QoL assessments ➤ Patient who is unwilling to have blood drawn for AZD7442 serum concentration at least 5 times ➤ Patient who is unwilling to have blood drawn twice for T-cell assay ➤ Patient whose native language is not English and does not have a person who can translate the regulatory documents, surveys and QoL assessments. ➤ Patient who is unable to provide Informed Consent or Authorization for Release of Health Information due to mental illness that requires a Legally Authorized Representative. ➤ Patient who is legally blind and does not have a witness/caregiver who has agreed to assist the patient in his/her participation in the study. ➤ Patient with a history of a severe allergic reaction (i.e., anaphylaxis) to any of the components of AZD7442 ➤ Patient with a history of severe allergic reaction (hypersensitivity) to any SARS-COV-2 vaccination, Polyethylene Glycol (PEG) or Polysorbate 80 ➤ Patient who is illiterate and does not have a witness/caregiver who has agreed to assist the patient in his/her participation in the study. ➤ Patient who is participating in an interventional trial for prophylaxis or treatment of SARS-CoV-2

9.0 Study Activities
	
9.1 Screening Activities
 
Total study enrollment will be based on approximately 80% of qualified enrolled subjects treated for solid tumors and approximately 20% of qualified enrolled subjects treated for hematologic malignancy.
 
 ➤ At the time of screening, all patients have (1) completed an FDA EUA or approved (Janssen, Moderna or Pfizer) COVID-19 single dose vaccine regimen, a two-dose vaccine regimen or one dose of a two-dose vaccine regimen; and/or (2) decided to receive or not receive an additional “booster” dose of Moderna, Pfizer or Janssen SARS-CoV-2 vaccine.

- In vaccinated patients, screening may occur at any time after 14 days post vaccination.
- Site personnel will draw blood for SARS-CoV-2 specific RBD-IgG antibody level at least 4 weeks or longer after completion of the most recent dose of any FDA approved SARS-CoV-2 vaccine.
- Blood drawn for SARS-CoV-2 RBD-IgG in all patients will be sent to LabCorp for analysis.

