23.4 AZD7442

AZD7442 (Evusheld) is a combination of two long-acting antibodies (LAABs) - tixagevimab (AZD8895) and cilgavimab (AZD1061) - derived from B-cells donated by convalescent patients after SARS-CoV-2 virus. Discovered at Vanderbilt University Medical Center and licensed to AstraZeneca in June 2020, the human monoclonal antibodies bind to distinct sites on the SARS-CoV-2 spike protein and were engineered and optimized by AstraZeneca with half-life extension and reduced Fc receptor and complement C1q binding. The half-life extension more than triples the durability of its action compared to conventional antibodies and could afford up to 12 months of protection from SARS-CoV-2 infection following a single administration. The reduced Fc receptor binding aims to minimize the risk of antibody-dependent enhancement of disease - a phenomenon in which virus-specific antibodies promote, rather than inhibit, infection and/or disease.

Data published in [*Nature*](#) in July 2020 showed in preclinical experiments that LAABs were able to block the binding of the SARS-CoV-2 virus to host cells and protect against infection in cell and animal models of disease.

23.5 AZD7442 Clinical Trial Results:

- AZD7442 is being studied in a comprehensive clinical trial program for both prevention and treatment of SARS-CoV-2 infection in over 9,000 participants. Ongoing trials include **TACKLE COVID-19**, a Phase III treatment trial in an outpatient setting and collaborator treatment trials in outpatient and hospitalized settings. **TACKLE** included 903 participants in a 1:1 randomization AZD7442 to placebo. AZD7442 is the first LAAB with Phase III data to demonstrate benefit in both prophylaxis and treatment of SARS-CoV-2 infection and is easily administered by IM injection. 90% of enrolled participants were from populations at high risk of progression to severe COVID-19, including those with co-morbidities. The primary analysis was based on 822 participants.
- AZD7442 was assessed using both IM and IV administration routes. Positive high-level results from the **TACKLE** Phase III COVID-19 treatment trial showed AstraZeneca's AZD7442, a long-acting antibody (LAAB) combination, achieved a statistically significant reduction in severe SARS-CoV-2 infection or death compared to placebo in non-hospitalized patients with mild-to-moderate symptomatic SARS-CoV-2 infection.

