23.6 Population AZD7442 Pharmacokinetic Data

A Phase I pharmacokinetic trial of AZD7442 was conducted in 48 healthy volunteers in the UK in August 2020. A Phase I, double-blind, placebo-controlled pK trial in 40 healthy Japanese volunteers is currently ongoing in Japan. The results of the UK study are not yet published.

23.7 Potential Benefits of AZD7442 Treatment in Immunosuppressed Patients Without Adequate COVID-19 RBD-IgG Antibody Protection

- AZD7442 reduces the risk of hospitalization or death when given to “at risk” patients as pre-exposure prophylaxis for prevention of SARS-CoV-2 infection. Infusion of this antibody mimics naturally produced antibodies generated by subjects infected with the SARS-CoV-2 virus. It is important to systematically evaluate whether use of AZD7442 for prevention of SARS-CoV-2 infection in immunosuppressed patients is protective against the SARS-CoV-2 virus in patients who have low or no antibody response to a COVID-19 vaccine or who, for a myriad of reasons, have not been adequately treated with a COVID-19 vaccine regimen. In patients treated with hematologic malignancy, active, significant immunosuppression is expected and as a result, there will be reduced protection against SARS-CoV-2 infection.
- This Real-World Evidence study will compare the incidence of symptomatic SARS-CoV-2 infection as well as SARS-CoV-2 related hospitalization and/or SARS-CoV-2 related death in all cancer patients treated with AZD7442 600 mg IM or IV. In addition, the study will compare Quality-of-Life metrics in all cancer patients treated with AZD7442 600 mg IM or IV as well as compare the same Quality-of-Life metrics between solid tumor and hematologic malignancy. To date, 300 mg IM has been tested as the dose for prevention while 600 mg IM has been tested as the dose for treatment post-infection, however, a recent FDA decision has requested that the dose of AZD7442 be increased to 600 mg for prevention.

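### Unless the assay is shown not to detect AZD7442, RBD-IgG measured after dosing may include the drug, so analyses using it cannot be read as describing the patient's own antibody

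*Protocol*

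**What the plan says.** **The drug.** Protocol 23.4 states that "the human monoclonal antibodies bind to distinct sites on the SARS-CoV-2 spike protein", and 23.7 adds: "Infusion of this antibody mimics naturally produced antibodies". All patients receive it (5.1), at baseline and again at Day 180 (9.3).

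**The assay.** RBD-IgG is the protocol's name for antibody to spike. Section 23.3 uses it that way for the response to vaccination, and 14.3 refers to "spike antibody (SARS-CoV-2 RBD-IgG) data". Sections 9.1 and 9.3 name the testing laboratory. They do not describe the assay, its behaviour in the presence of AZD7442, or any correction.

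**The schedule.** RBD-IgG is drawn at baseline and on Days 90, 180, 270 and 360 (5.5), and again after a positive RT-PCR (9.3). AZD7442 concentration is measured on Days 30, 90, 180, 270 and 360.

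**The analyses.**
- 2.2 expects that "serum concentration of AZD7442 may be correlated with IgG antibody level to SARS-CoV-2", and 17.8 plans to assess how AZD7442 concentration, RBD-IgG and T-cell function relate.
- 14.3, first endpoint, concerns the level of immunity over time "provided by a combination of AZD7442 and antibodies that developed in response to prior SARS-CoV-2 vaccination or infection in this population".
- 14.3, second endpoint, compares pre-event AZD7442 concentration and RBD-IgG between patients with and without infection.
- 15.1 lists "RBD-IgG levels for all patients with comparisons between disease category" among the interim secondary analyses.
- 17.5 bases RBD-IgG correlations on complete data and does not limit them to baseline.

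**Baseline timing.** Section 9.1 says "screening may occur at any time after 14 days post vaccination", but also requires the blood draw for "RBD-IgG antibody level at least 4 weeks or longer after completion of the most recent dose".

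**The concern.** A test for human IgG against the spike's receptor-binding domain, run on serum that holds 600 mg doses of human anti-spike IgG, may report the sum of injected and host antibody. Relating that sum to AZD7442 concentration relates a total to one of its parts, so a positive correlation can appear with no biological link behind it. A solid tumor versus hematologic difference in post-dose RBD-IgG could likewise reflect a difference in drug exposure. In the pre-event comparison of 14.3, the two measures would not be separate pieces of evidence.

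At stake is what the trial can say about host antibody. Host antibody is the background question of 23.2, and the interim results on it go to the Data Monitoring Committee (21.1). A later statistical plan cannot fully repair this, because the mixing would be in the sample and the assay.

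**Working it through.** The protocol gives no figure on this point to reproduce. The check traces what is measured, when, and how it is used, and then illustrates the size.

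**1. Timing of the draws**

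| RBD-IgG draw | Relation to AZD7442 | AZD7442 also measured that day |
|---|---|---|
| Baseline | before first dose (9.1) | no |
| Day 90 | after dose 1 | yes |
| Day 180 | after dose 1; order against dose 2 not stated | yes |
| Day 270 | after both doses | yes |
| Day 360 | after both doses | yes |
| After positive RT-PCR | after dosing | yes |

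Four of five scheduled draws are post-dose. At full enrolment that is 4 × 1,500 = 6,000 of 5 × 1,500 = 7,500 samples. This shows exposure to the problem, not the amount of bias.

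**2. Is drug still present?** Section 23.4 speaks of up to 12 months of protection from one administration but gives no half-life. Assume first-order decay, with the share of the initial level equal to 0.5^(t/h), and add the Day 180 dose where it applies.

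| Assumed half-life h | Day 90 | Day 180, before redosing | Day 270 | Day 360 |
|---|---|---|---|---|
| 30 days | 12.5% | 1.6% | 13% | 1.6% |
| 60 days | 35% | 12.5% | 40% | 14% |
| 90 days | 50% | 25% | 63% | 31% |

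For example, at h = 60 on Day 270: 0.5^(270/60) + 0.5^(90/60) = 0.044 + 0.354 = 0.398.

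**3. Correlation by construction.** Assume the assay reads both sources alike, so measured = host + drug, with host and drug independent. Then

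r(measured, drug) = SD_drug / √(SD_drug² + SD_host²).

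SD_drug is 25 mcg/ml, the planning value in 17.2. SD_host is not given and is assumed over a range.

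| Assumed SD_host (mcg/ml) | r |
|---|---|
| 5 | 25/√(625 + 25) = 0.98 |
| 10 | 25/√(625 + 100) = 0.93 |
| 25 | 25/√(625 + 625) = 0.71 |
| 50 | 25/√(625 + 2,500) = 0.45 |
| 100 | 25/√(625 + 10,000) = 0.24 |

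The true host-drug correlation is zero in every row.

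**4. Group comparison.** Under the same assumption, the difference in mean RBD-IgG equals the host difference plus the drug difference. A drug difference of 5 mcg/ml, the margin in 17.2, would add 5 mcg/ml to the RBD-IgG difference. Whether that is large depends on the host level, which is not stated. The interim follows the 6-month assessments, so its scheduled draws are baseline (drug-free) and Days 90 and 180 (not drug-free). Section 15.1 does not say which is compared.

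**5. Day 180.** The draw and the second dose each have a window of ±5 days (9.3). The draw may therefore fall from 10 days before the dose (Day 175 against Day 185) to 10 days after it (Day 185 against Day 175).

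**6. Baseline.** Sections 8.1 and 9.1 allow entry from 14 days after vaccination. Sections 5.2 and 9.1 place the RBD-IgG draw at 4 weeks or later. A patient at 14 to 27 days satisfies the first rule but cannot yet have a draw that satisfies the second. Section 17.4 requires this baseline value for the ITT population.

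**The case against.** The strongest objection is that interference is inferred. The protocol says the drug binds spike, not that it binds the receptor-binding domain, and it does not describe the assay. This stands, and it is why the point is conditional. A reader might infer that the analyses cannot be derived at all. The document does not support that: evidence that the assay does not detect AZD7442, or a validated correction, would restore them.

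A reader might also take the first endpoint of 14.3 as splitting protection between drug and host antibody. It does not. It describes a combined effect, does not name RBD-IgG, and could draw on the baseline sample for vaccination or infection before entry.

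It can be said that 2.2, 15.1 and 17.8 never call post-dose RBD-IgG the patient's own antibody. That is true, but they analyse it beside AZD7442 concentration, or between cancer types, without saying what else it could be. The spike-antibody label in 14.3 belongs to a baseline profile, so it supports the terminology and is not itself a faulty use.

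It would be too strong to say that a post-dose group difference largely repeats the drug difference. The range 0.24 to 0.98 shows that this turns on an unstated variance ratio, and an SD of 25 with a margin of 5 does not fix a mean drug level.

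The 14-day and 4-week rules can both be met by screening early and drawing later, because 9.1 makes the draw a step before dosing. The passages still need to agree, since this is the only drug-free sample. Section 9.1 already puts that draw before treatment, so nothing needs adding there.

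**Conclusion.** The point holds conditionally. On the protocol's own description, RBD-IgG on Days 90, 180, 270 and 360, and after infection, may contain drug plus host antibody. Unless non-interference is shown, four uses cannot be read as findings about host antibody: the drug-IgG relationship in 2.2 and in 17.8, the second endpoint of 14.3, and any post-dose comparison under 15.1.

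The size is not fixed by the document. Under equal assay reading and independence, the artificial correlation runs from 0.24 to 0.98 for assumed host SDs of 100 down to 5 mcg/ml. Severity is moderate, because the affected analyses are exploratory, interim-secondary or sub-study, plus one hypothesis stated as a possibility. A reader might fear for the main results, but the primary endpoint is AZD7442 concentration itself and no secondary endpoint in 14.1 uses RBD-IgG. The baseline sample remains valid as a host measure.

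**What to change.** - In 2.2, 14.3 (second endpoint), 15.1 and 17.8, name pre-dose RBD-IgG as the measure of host antibody.
- Document whether the assay detects AZD7442. Unless non-interference is shown, label all post-dose values as total anti-RBD IgG (host plus AZD7442), report them descriptively, and do not treat them as independent of AZD7442 concentration.
- On the same condition, restrict the correlation in 2.2 to pre-dose RBD-IgG or withdraw it.
- State whether the Day 180 draw comes before or after the Day 180 dose.
- Reconcile the 14-day passages (8.1, 9.1) with the 4-week passages (5.2, 9.1) that bear on the baseline draw.

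**Cost.** These are wording changes plus an enquiry to the laboratory; no new samples are needed. Post-dose RBD-IgG results become descriptive. The host response to vaccine doses given after baseline, which 5.4 allows, would not be captured by the pre-dose sample.
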